11.2.2. Serious Adverse Events

An AE is considered serious if, in the view of either the investigator or sponsor, it fulfills at least one of the following:

- Results in death;
- It is immediately life-threatening;
- It requires in-patient hospitalization or prolongation of existing hospitalization;
- It results in persistent or significant disability or incapacity;
- Results in a congenital abnormality or birth defect;
- It is an important medical event that may jeopardize the subject or may require medical intervention to prevent one of the outcomes listed above.

All SAEs that occur after any subject has been consented, before treatment, during treatment, or up to and including the End of Study or Early Termination Visit, whether or not they are related to the study, must be recorded on forms provided by Hepion.

11.2.3. Other Adverse Events

Other AEs will be identified by the investigator and if applicable also by the medical monitor during the evaluation of safety data for the Clinical Study Report. Adverse events of special interest, other than SAEs or AEs leading to discontinuation of the subject from the study, will be classified as other AEs. For each of these other AEs, a narrative may be written and included in the Clinical Study Report.

11.3. Relationship to Study Drug

An investigator who is qualified in medicine must make the determination of relationship to the investigational product, when appropriate, for each AE (unrelated, possibly related or probably related). The investigator should decide whether, in his or her medical judgment, there is a reasonable possibility that the event may have been caused by the investigational product. If no valid reason exists for suggesting a relationship, then the AE should be classified as “unrelated.” If there is any valid reason, even if undetermined, for suspecting a possible cause and effect relationship between the investigational product and the occurrence of the AE, then the AE should be considered “related.”

If the relationship between the AE/SAE and the investigational product is determined to be “possible” or “probable” the event will be considered to be related to the investigational product for the purposes of expedited regulatory reporting.

11.4. Recording Adverse Events

Adverse events spontaneously reported by the subject and/or in response to an open question from the study personnel or revealed by observation will be recorded during the study at the investigational site. Clinically significant changes in laboratory values, blood pressure, and pulse requiring an intervention should be reported as AEs. The AE term should be reported in standard medical terminology when possible. For each AE, the investigator will evaluate and report the onset (date and time), resolution (date and time), severity, causality, action taken, serious outcome (if applicable), and whether or not it caused the subject to discontinue the study.

Adverse events should be collected and recorded in the source documents and on the eCRF beginning at the time of signing the informed consent. Adverse events and SAEs should be reported through End of Study Visit or Early Termination Visit. Both AEs and SAEs should be followed until resolution/stabilization or until a time that is mutually agreed upon between the medical monitor and investigator.

Subjects who experience any AE or SAE should receive appropriate treatment and medical supervision as clinically indicated.

All AEs will be graded for severity according to the Common Terminology Criteria for Adverse Events table v5.0 ([CTCAE, 2017](#)).

It is important to distinguish between serious and severe AEs. Severity is a measure of intensity whereas seriousness is defined by the criteria under Section 11.2.2. An AE of severe intensity may not be considered serious.

Should a pregnancy occur, it must be reported and recorded on Hepion's pregnancy form. Pregnancy, in itself, is not regarded as an AE unless there is a suspicion that an investigational product may have interfered with the effectiveness of a contraceptive medication.

The outcome of all pregnancies (spontaneous miscarriage, elective termination, normal birth or congenital abnormality) must be followed up and documented even if the subject was discontinued from the study.

All reports of congenital abnormalities/birth defects are SAEs. Spontaneous miscarriages should also be reported and handled as SAEs. Elective abortions without complications should not be handled as AEs.

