7.1.3. Follow Up Period

After completion of the treatment period, the subjects will be monitored for additional 14 days. A visit window of ± 2 days will be allowed for the Day42/EOS visit.

Subjects who do not complete the study may be replaced within a dosing cohort, unless a stopping rule precludes replacement. Safety criteria for dose adjustments or stopping rules are provided in [Section 7.5](#).

The overall study design of all scheduled procedures is shown in [Table 3](#).

Table 3: Schedule of Events

Procedure	Screening (Day -30 to -2)	Day -1	Day 1	Day 2	Day 7 (±1)	Day 14 (±1)	Day 28 (+2)	EOS/ Day 42 (±2)	ET ^a
Informed Consent ^b	X								
Demographics	X								
Weight and height	X								
HIV, HBV, HCV tests	X								
Physical exam	X								
Medical history	X								
Inclusion/exclusion	X	X							
Randomization		X							
Pregnancy test ^c	X	X						X	X
FSH	X								
Drugs of abuse and alcohol screen	X	X							X
Vital signs ^d	X	X	X	X	X	X	X	X	X
ECG ^e	X	X	X	X	X	X	X	X	X
Blood chemistry ^f	X	X	X	X	X	X	X	X	X
Hematology and Coagulation	X	X	X	X	X	X	X	X	X
Urinalysis	X	X	X	X	X	X	X	X	X
PK ^g			X			X	X		X ^h
Fraction Unbound ^g			X				X		
ELF Score	X						X		

^k On Day 1 and Day 28, subjects will fast overnight for at least 8 hours, will take CRV431 or matching placebo and will fast for an additional 2 hours following receipt of study drug. On subsequent days subject will fast overnight for at least 8 hours, will take CRV431 or matching placebo and will fast for an additional 30 minutes following receipt of study drug.

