8.3. Subject Withdrawal Criteria

8.3.1. Early Termination of Subjects from the Study

Subjects who discontinue the study should complete all scheduled safety assessments at the Early Termination Visit. If an Early Termination Visit and a scheduled visit coincide, procedures for both visits should be completed, without duplication. Subjects must discontinue the study for the following reasons:

- Subject withdraws consent;
- Subject unwilling or unable to follow study procedures, per judgment of the investigator;
- Investigator, sponsor, or Regulatory Authority judge that further dosing with study drug would be harmful to the subject;
- Subject experiences an SAE that is judged, by the investigator and the sponsor, to be related to study drug;
- Subject experiences a Grade 3 CTCAE AE judged, by the investigator and the sponsor, to be related to study drug;
- Subject experiences a Grade 4 CTCAE AE judged, by the investigator and the sponsor, regardless of the relation to study drug;
- Subject experiences a Grade 3 or Grade 4 CTCAE laboratory abnormality judged by the investigator and the sponsor, to be related to study drug except for asymptomatic elevations in cholesterol or triglycerides which are accepted;

- Subject with normal ALT and bilirubin at baseline who experiences confirmed, non-cholestatic ALT $>3 \times$ ULN and bilirubin $>2 \times$ ULN OR subjects with elevated ALT at baseline who experiences confirmed, non-cholestatic ALT $>10 \times$ baseline value and bilirubin $>2 \times$ ULN;
- Subject experiences a confirmed,
 - QTcF interval 500 msec;
OR
 - QTcF interval change from baseline ≥ 60 msec that has an absolute value ≥ 480 msec. The value of an individual ECG time point is the average of the triplicate values
 - “confirmed” is defined as the abnormality duplicated, at least 1 hour after the abnormality is first noted, by the results of a set of 3 ECGs performed in triplicate, at least 5, but not more than 10 minutes between each assessment;
- Subject experiences any hepatic AE or SAE judged by the investigator or sponsor as DILI and to be related to study drug and not to the subject’s underlying NASH.

Subjects who discontinue the study due to the safety stopping criteria will be replaced if the investigator and sponsor agree and the criteria outlined in Section 7.5 are not violated. Subjects who discontinue the study for non-safety reasons may be replaced.

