If a subject is withdrawn from the study the reason(s) for withdrawal must be documented in the subject’s medical record and CRF. An Early Termination Visit should be performed. All subjects must be followed for safety until the time of the follow-up evaluation or until study drug related toxicities resolve, return to baseline or are deemed irreversible, whichever is longer.

Subjects who cannot be reached after 3 documented attempts to be contacted to schedule a follow-up visit will be considered lost to follow up.

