11.2. Adverse and Serious Adverse Events

11.2.1. Adverse Events

An AE is defined as any untoward medical occurrence in a clinical study subject associated with the use of a drug (investigational or non-investigational) in humans, whether or not considered drug related. An AE can be any unfavorable and unintended sign (e.g., an abnormal laboratory

finding), symptom, or disease temporally associated with the use of a drug, without any judgement on causality. An AE can arise from any use of the drug (e.g., off-label use, use in combination with another drug) and from any route of administration, formulation, or dose, including overdose.

All AEs that occur after any subject has been consented, before treatment, during treatment, or up to and including the End of Study or Early Termination Visit, whether or not they are related to the study, must be recorded on forms provided by Hepion.

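### New adverse events that start after an Early Termination visit fall outside the recording window, although completers are recorded for 14 days after the last dose and Protocol 8.3.1 requires longer safety follow-up

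*Combined protocol and SAP*

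**What the plan says.** **Recording limit.** Protocol 11.4 ends collection as follows: "Adverse events and SAEs should be reported through End of Study Visit or Early Termination Visit". Section 11.2.1 has AEs recorded "up to and including the End of Study or Early Termination Visit". Section 11.2.2 repeats this for SAEs, and SAP 7.2 carries it into the analysis plan.

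**Completers.** Protocol 7.1.3: "After completion of the treatment period, the subjects will be monitored for additional 14 days". The closing visit is Day 42 ± 2.

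**Subjects who leave early.** Section 8.3.1 lists reasons for mandatory exit from the study. One is "Subject experiences a Grade 3 CTCAE AE judged, by the investigator and the sponsor, to be related to study drug". Others are a related SAE, any Grade 4 event, confirmed QTcF prolongation and drug-induced liver injury. These subjects have an ET visit. The same section then says "All subjects must be followed for safety until the time of the follow-up evaluation or until study drug related toxicities resolve, return to baseline". A judgement that the toxicity is permanent also ends this follow-up, and the later end point applies. The follow-up evaluation is not defined.

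**Events already on record.** Section 11.4 continues: "Both AEs and SAEs should be followed until resolution/stabilization or until a time that is mutually agreed upon". Section 11.5 says the same for SAEs.

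**Analysis.** SAP 7.2.5 divides the number of subjects with an event by the whole Safety Set. SAP 4.4 imputes nothing.

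**The concern.** Safety and tolerability against placebo is a primary objective. The recording rule gives two lengths of post-dose observation: two weeks for those who finish, and only the time from last dose to ET visit for those who do not. Some of the second group are there because the protocol removed them for toxicity.

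Section 8.3.1 asks for safety follow-up past ET, but no readable section tells a site to record an AE that first appears during it. Such an event may never reach the database. The SAP would then show the subject as free of that event, with no allowance for the shorter observation. The stopping rules in 7.7.2 and 7.7.2.1 turn on counts of one, two or three subjects, so a single unrecorded event could matter there too.

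**Working it through.** **1. Follow-up for completers**

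Inputs: last dose Day 28, window +2 (Protocol 7.1.2); closing visit Day 42 ± 2 (7.1.3).

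- Nominal: 42 − 28 = 14 days, which agrees with the stated 14.
- Shortest under the windows: 40 − 30 = 10 days.
- Longest: 44 − 28 = 16 days.

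**2. Follow-up for early terminators**

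New events are recorded only for the lag L between last dose and ET visit. The readable text does not give L, so it is assumed over a range. Nominal shortfall = 14 − L; with visit windows, (10 − L) to (16 − L).

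| Assumed lag L (days) | Nominal shortfall (days) | Range with windows (days) |
|---|---|---|
| 0 | 14 | 10 to 16 |
| 1 | 13 | 9 to 15 |
| 2 | 12 | 8 to 14 |
| 7 | 7 | 3 to 9 |

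**3. The collection and follow-up rules compared**

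| Event in a subject who has had an ET visit | Rule that applies | Covered? |
|---|---|---|
| AE or SAE present at ET | 11.4, 11.5, 8.3.1: follow to resolution, stabilization or an agreed time | Yes |
| AE that starts after ET | 8.3.1 requires follow-up; 11.2.1, 11.4 and SAP 7.2 end recording at ET | No recording instruction |
| SAE that starts after ET | As above, with 11.2.2; 11.5 requires a report within 24 hours of the investigator becoming aware and states no ET limit | Ambiguous |

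The SAP would not itself exclude a late event: SAP 7.2.1 puts no upper time limit on a TEAE. SAP 7.2.5 takes events before the end of study, without saying whether that means the subject's own exit or Day 42. The restriction lies in the collection rule.

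**4. What the tables could miss**

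SAP 7.2.5 counts subjects, not episodes, outside the overall summary. A subject removed for a Grade 3 related AE is already in the any-TEAE count. A new event after ET could still add:

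- another preferred term or system organ class;
- a higher maximum severity;
- a first treatment-emergent SAE, if the exit event was not serious.

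A subject who left for a non-safety reason with no prior TEAE could also be missed from the any-TEAE count.

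Each active arm has 12 subjects, so one missed subject moves an incidence row by 1/12 = 8.3 percentage points. Replacement under 8.4 does not remove the early leaver from the Safety Set, which is everyone dosed (Protocol 12.2.2, SAP 4.2.2).

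**The case against.** The strongest reply is that the protocol does not abandon these subjects. Sections 8.3.1, 11.4 and 11.5 all carry follow-up past ET, and the event that caused the stop is both followed and counted. That stands, and it limits the point to new-onset events. The conflict could narrow further if the follow-up evaluation in 8.3.1 was meant to be the ET visit. But 8.3.1 names the ET visit separately and then speaks of scheduling a follow-up visit, so the more natural reading is that they differ. Either way the term needs a definition.

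Four stronger readings are tempting and are not supported:

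- **That subjects who stop for toxicity lose their follow-up.** They do not, for the reasons just given. Nor is every drug stop a study exit: 7.7.1 provides for discontinuing or interrupting drug without stating that the subject leaves, and such a subject could remain to Day 42.
- **That a Day 7 stopper loses 83% of the recording period (35 of 42 days) and all 14 post-dose days.** Both figures assume an ET visit on the last dosing day, which the readable text does not say.
- **That TEAE and SAE incidence on CRV431 is biased downward.** The direction is plausible. Investigator and sponsor are unblinded (7.3.3), and several exit criteria need both to judge the event related, which is less likely for a known placebo subject. But Grade 4 events force exit regardless of relation, no expected number of exits is given, and the any-TEAE count already includes those removed for an AE.
- **That drug persists for exactly the unrecorded time.** The 75 mg levels in Protocol 5.3 give an effective half-life of about 37 h from peak to trough over 24 h (1397.5 to 889.5 ng/mL), and about 61 h from accumulation (1397.5/334 = 4.18). Five half-lives would be about 7.7 to 12.7 days. Both rest on a one-compartment model and differ by a factor of about 1.7. Any overlap again depends on ET timing.

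**Conclusion.** The point holds for new-onset AEs and SAEs after ET in subjects who leave the study, including those removed under the toxicity criteria in 8.3.1. For them the recording rule is shorter than the one for completers and does not fit the follow-up that 8.3.1 requires. The shortfall is up to 14 nominal post-dose days, and 7 to 14 days over assumed ET lags of 7 to 0 days. The tables most exposed are those by preferred term, highest severity and SAE, along with the small-count stopping rules. The effect on the comparison with placebo is plausible but cannot be quantified from the documents, because neither the number of early exits nor the ET timing is given. This is a cheap improvement, not a flaw that undermines the trial.

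**What to change.** Reconcile Protocol 11.2.1, 11.2.2 and 11.4 and SAP 7.2 and 7.2.5 with Protocol 8.3.1:

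- Record new-onset AEs and SAEs for every dosed subject through 14 days after the last dose, whether or not an ET visit has taken place, by telephone if the subject does not attend.
- Define the follow-up evaluation in 8.3.1 as that 14-day contact, and state when the ET visit takes place relative to the last dose.
- In SAP 7.2.5, replace the end-of-study limit with the same window.

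Fourteen days after the last dose matches completers. Running to Day 42 for everyone would go beyond parity: a subject who stopped on Day 7 would have 42 − 7 = 35 post-dose days against 14.

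The cost is a sentence in each section and one further contact per early terminator, within follow-up that 8.3.1 already requires. Subjects who withdraw consent to further contact would remain unobserved and should be reported as such.

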11.5. Reporting Adverse Events

Serious adverse events must be reported to the Sponsor within 24 hours of the investigator becoming aware of the event along with an assessment of causality. If at the time the investigator submits an initial SAE report and the SAE has not been resolved, the investigator must provide a follow-up report as soon as the event resolves (or upon receipt of significant information if the event is still ongoing). Additional follow-up information, if required or available, should be reported to the Sponsor within one business Day of receipt. This should be completed on a follow-up SAE form and placed with the original SAE information and kept with the appropriate section of the CRF and/or study file.

All SAEs must be followed until resolution/stabilization or until a time that is mutually agreed upon between the Medical Monitor and the Investigator.

Hepion (or representative) is responsible for notifying the relevant regulatory authorities of certain events. It is the Investigator's responsibility to notify the IRB or IEC of all SAEs that occur at his or her site. Investigators will also be notified of all unexpected, serious, drug-related events that occur during the clinical trial. Each site is responsible for notifying its IRB or IEC of these additional SAEs.

12. STATISTICS

12.1. Sample Size Determination

The sample size selected for each population to evaluate the effect of NASH F2/F3 on the PK of CRV431 was not chosen to satisfy any *a priori* statistical requirement. This sample size of a total of 36 subjects (12 active with 6 matching placebo at each dose level) has historically been shown to be sufficient for studies of this type and should provide adequate data to support the planned analyses.

12.2. Population for Analyses

12.2.1. Pharmacokinetic Population

Samples from all subjects will be assayed even if the subjects do not complete the study. All subjects who comply sufficiently with the protocol and display an evaluable PK profile (e.g., exposure to treatment, availability of measurements and absence of major protocol violations) will be included in the statistical analyses.

12.2.2. Safety Population

All subjects who received the study drug or placebo will be included in the safety evaluations.

12.3. Statistical Analyses

[REDACTED]

[REDACTED]

[REDACTED]

12.3.1. Interim Safety Review

An interim safety review will be performed when at least six (6) subjects in Cohort A (CRV431 75 mg) and at least three (3) subjects in Cohort B (matching placebo) have reached 28 days of dosing. A minimum of 28 days of safety data and any available PK data will be reviewed by an independent DSMB. Dosing of Cohort C (CRV431 225mg) and Cohort D (matching placebo) may proceed if agreement of the DSMB has been received and no stopping rules have been met. The DSMB will also review the Day 28 safety data from the remaining subjects to confirm there are no changes to the prior safety assessment. For the purpose of the interim safety review, dosing in Cohort A and Cohort B will not be paused during this DSMB review.

12.3.2. Analysis of Covariance

Placebo subjects will be used for comparison with all presumed NASH treatment subjects using the following analysis.

An analysis of covariance (ANCOVA) will be performed on the ln-transformed AUC_{0-inf} and C_{max} . The ANCOVA model will contain a categorical factor of population (for subjects with F2/F3 presumed NASH, and F2/F3 presumed NASH placebo subjects), a categorical covariate (sex), and continuous covariates (age, weight, BMI and ideal body weight).

The comparisons of interests are:

- CRV431-treated F2 presumed NASH subjects versus placebo treated F2 presumed NASH subjects stratified by dosing cohort, i.e. Cohort A (75 mg QD) versus Cohort C (225 mg QD);
- CRV431-treated F3 presumed NASH subjects versus placebo treated F3 presumed NASH subjects stratified by dosing cohort, i.e. Cohort A (75 mg QD) versus Cohort C (225 mg QD);
- CRV431-treated pooled F2/F3 presumed NASH subjects versus pooled placebo treated F2/F3 presumed NASH subjects stratified by dosing cohort will only be evaluated for differences [REDACTED]

A full covariate population PK/PD model will be developed for exploratory purposes.

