9.2 Placebo

The placebo for this study utilizes the same formulation, white opaque, oblong softgel capsule without marking and without the active ingredient of CRV431 drug substance.

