10.4. Whole Blood Pharmacokinetic Parameters

Pharmacokinetic parameters for the measurement of CRV431 and its metabolites will be performed from whole blood and are shown in Table 5.

Table 5: Pharmacokinetic Parameters

Parameter	Definition
[REDACTED]	[REDACTED]
[REDACTED]	[REDACTED]
[REDACTED]	[REDACTED]
[REDACTED]	[REDACTED]
[REDACTED]	[REDACTED]
[REDACTED]	[REDACTED]
[REDACTED]	[REDACTED]
[REDACTED]	[REDACTED]
[REDACTED]	[REDACTED]
[REDACTED]	[REDACTED]
[REDACTED]	[REDACTED]
[REDACTED]	[REDACTED]
[REDACTED]	[REDACTED]
[REDACTED]	[REDACTED]
[REDACTED]	[REDACTED]
[REDACTED]	[REDACTED]
[REDACTED]	[REDACTED]
[REDACTED]	[REDACTED]

[REDACTED] No PK parameters will be calculated for subjects with 2 or fewer consecutive time points with detectable concentrations. Individual and mean whole blood concentration time curves (both linear and log-linear) will be

[REDACTED]

Table 6: Pharmacokinetic Sampling Schedule

Day	Day 1				Day 14	Day 28			
Time (h)	Pre-dose	2.0	4.0	8.0	312 (Pre-dose)	Pre-dose	2.0	4.0	8.0
Whole blood (PK)	X	X	X	X	X	X	X	X	X
Plasma (f_u)	X	X				X	X		

Abbreviations: f_u , fraction unbound; h, hour; PK, pharmacokinetic(s).

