12.3.3. Ratios and Confidence Intervals

Ratios of least-squares means (LSM) will be calculated using the exponentiation of the difference between F2/F3 presumed NASH groups LSM from the analyses on the ln-transformed

AUC_{0-inf} and C_{max} . These ratios will be expressed as a percentage relative to the F2/F3 presumed NASH placebo control group.

Ninety percent (90%) confidence intervals (CIs) for the ratios will be derived by exponentiation of the CIs obtained for the difference between F2/F3 presumed NASH groups LSM resulting from the analyses on the ln-transformed AUC_{0-inf} and C_{max} . The CIs will be expressed as a percentage relative to the F2/F3 presumed NASH placebo control group.

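### Placebo is the reference group for the CRV431 AUC0-inf and Cmax ratios, but placebo subjects have no CRV431, so neither the ratios nor their 90% CIs can be estimated

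*Combined protocol and SAP*

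**What the plan says.** Protocol section 12.3.2 opens with the instruction that "Placebo subjects will be used for comparison with all presumed NASH treatment subjects using the following analysis". The analysis that follows is an ANCOVA on ln-transformed AUC0-inf and Cmax. Its only treatment term is a "categorical factor of population (for subjects with F2/F3 presumed NASH, and F2/F3 presumed NASH placebo subjects"), with sex, age, weight, BMI and ideal body weight as covariates. The first listed comparison sets CRV431-treated F2 subjects against "placebo treated F2 presumed NASH subjects stratified by dosing cohort, i.e. Cohort A (75 mg QD) versus Cohort C (225 mg QD"). The second does the same for F3, and the third pools the stages.

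Section 12.3.3 names the denominator twice. For the least-squares-mean ratios: "These ratios will be expressed as a percentage relative to the F2/F3 presumed NASH placebo control group". For the 90% intervals: "The CIs will be expressed as a percentage relative to the F2/F3 presumed NASH placebo control group".

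Other sections determine whether a placebo subject can have a value:

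- Protocol 9.2: the placebo capsule is "without marking and without the active ingredient of CRV431 drug substance".
- Protocol 10.3: the PK assay measures CRV431, with its major metabolites examined qualitatively.
- Protocol 10.4: "No PK parameters will be calculated for subjects with 2 or fewer consecutive time points with detectable concentrations".
- Protocol 12.2.1: the PK population is "All subjects who comply sufficiently with the protocol and display an evaluable PK profile". SAP 4.2.1 repeats this definition.
- SAP 4.4: missing values stay missing, without imputation.

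**The concern.** A ratio of drug exposure needs exposure in both groups. Placebo subjects are given no CRV431, so they have neither a Cmax nor an AUC to put in the denominator, and the logarithm of zero is undefined.

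PK is one of the two primary objectives (protocol 6.1, SAP 2.1.1), and 12.3.2–12.3.3 hold the only inferential PK analysis visible in the public documents. The Synopsis lists Cohort A versus Cohort C among its planned comparisons, and that PK contrast can be estimated. The model in 12.3.2 has no dose term, however, and 12.3.3 defines no Cohort C to Cohort A ratio.

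If the written analysis cannot run, whoever does the analysis must choose the model, reference group and normalisation afterwards. Under section 7.3.3 the sponsor and investigators know the treatment assignments.

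**Working it through.** The plan gives no power or effect-size figure on this point. The only figure to reproduce is the count in section 12.1: 2 × (12 + 6) = 36.

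**1. Placebo subjects with a PK value.** Cohorts B and D have 6 each, 12 in total. With no CRV431 in the capsule there should be no detectable time points. Section 10.4 then gives no PK parameter, 12.2.1 gives no evaluable profile, and SAP 4.4 fills nothing in. Analysable: 0 of 12 overall, and 0 of 6 at each dose.

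**2. Is the contrast estimable?** The written model has 7 columns: intercept, population, sex, age, weight, BMI, ideal body weight. Covariate values were simulated; they do not affect the result for the population column.

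| Rows used | Columns | Rank | Active minus placebo |
|---|---|---|---|
| All 36, if every subject had a value | 7 | 7 | estimable |
| 24 active only | 7 | 6 | not estimable |
| 12 active in one dose cohort | 7 | 6 | not estimable |

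On the active rows the population column equals the intercept, hence the lost rank. The F2-only and F3-only comparisons use fewer than a whole cohort wherever both stages are enrolled (the plan gives no stage counts). They still have no placebo values and fail in the same way.

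**3. Would substituting a value for placebo help?** The visible text has no such rule, and the assay limit is not given. The following is a sensitivity check on assumed placebo values only, using the 75 mg steady-state Cmax of 1397.5 ng/mL from section 5.3:

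- 5 ng/mL: 100 × 1397.5 / 5 = 27,950%
- 1 ng/mL: 100 × 1397.5 / 1 = 139,750%
- 0.5 ng/mL: 100 × 1397.5 / 0.5 = 279,500%

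The result simply scales with the number substituted. Constant placebo values also give no terminal slope from which to compute AUC0-inf.

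**4. What can be estimated.** Replacing population by dose cohort among the 24 active subjects gives rank 7 of 7, with 24 − 7 = 17 residual degrees of freedom (24 − 2 = 22 without covariates). The steady-state Cmax means in section 5.3 give 1844 / 1397.5 = 1.32 for a threefold dose, or 1.32 / 3 = 0.44 dose-normalised.

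To show the precision of 12 versus 12, assume lognormal data and read the ± figures in 5.3 as SDs, which the text does not state:

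- CVs: 97.8 / 1397.5 = 7.0% and 321.9 / 1844 = 17.5%
- ln-scale variances, ln(1 + CV²): 0.0049 and 0.0300
- ln ratio: ln(1.3195) − (0.0300 − 0.0049)/2 = 0.265, a geometric mean ratio of 1.30
- SE: √[(0.0049 + 0.0300)/12] = 0.054; t(0.95, 22 df) = 1.717
- 90% CI: exp(0.265 ± 1.717 × 0.054) = 1.19 to 1.43

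If the between-subject CV were 20%, 30% or 50% (assumed), the 90% CI around 132% would be 115–152%, 107–162% or 95–184%.

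**5. Does the sampling support AUC0-inf?** Post-dose samples are at 2, 4 and 8 hours (Table 6). Section 5.3 gives, for 75 mg, a single-dose Cmax of 334 and a steady-state Cmax and trough of 1397.5 and 889.5 ng/mL. Under a rough mono-exponential assumption:

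- From peak to trough, with the peak assumed at 2 h: k = ln(1397.5/889.5)/22 = 0.0205 per h, half-life about 34 h
- From accumulation: k = −ln(1 − 334/1397.5)/24 = 0.0114 per h, half-life about 61 h
- Share of AUC0-inf beyond 8 h, exp(−8k): about 85% to 91%

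Most of AUC0-inf would therefore be extrapolated, even in active subjects.

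**The case against.** The strongest reply is that little depends on this analysis. The study has no powered hypothesis, and both the Synopsis and section 12.1 say the sample size has no statistical basis. Sections 12.3.2 and 12.3.4 keep descriptive and population PK/PD analyses. The failure is also obvious: a model that returns nothing cannot mislead anyone. All of this stands, and the PK objective is not lost. It does not make the written instruction workable.

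A second reply is that the real analysis may lie in redacted text: the body of protocol 12.3, SAP 6.2, Table 5, and the end of the third comparison in 12.3.2 are blacked out. The visible SAP does not repeat this ANCOVA, and its table list shows no PK table. Other PK analyses may therefore exist. They would still sit beside an unredacted instruction that names placebo as denominator for both the ratios and the intervals.

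A third is that the dose comparison is already planned. The Synopsis does list A versus C, but 12.3.2 mentions those cohorts only as strata of the placebo comparison. This supports the correction.

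Finally, section 12.1 frames the sample around the effect of NASH F2/F3 on PK, which a dose ratio does not address. That is true, but all four cohorts have presumed NASH, so no between-group contrast in this trial addresses it.

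**Conclusion.** The analysis in 12.3.2–12.3.3 is wrong as written. With 0 of 12 placebo values, the active-versus-placebo contrast on ln AUC0-inf and ln Cmax cannot be estimated, whether overall, by dose or by fibrosis stage, and no ratio or 90% CI results. This rests on placebo subjects having no detectable CRV431 and on the visible text holding no substitution rule. Such a rule would only produce a ratio fixed by the substituted number. The fault is confined to PK parameters; placebo remains a valid comparator for safety and biomarkers. The Cmax ratio of 1.32, its intervals and the half-life range in the working are illustrations from section 5.3 under stated assumptions, not predictions for this trial.

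**What to change.** In protocol 12.3.2 and 12.3.3, and in any SAP text that carries the same analysis:

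1. Limit the ln-PK model to CRV431-treated subjects, with dose cohort (A or C) as the factor.
2. Define the estimate as the Cohort C to Cohort A geometric mean ratio, unnormalised and dose-normalised, with a 90% CI. This implements the comparison already listed in the Synopsis.
3. Apply it to Day 28 Cmax and to an AUC that the 0–8 h samples support, in place of AUC0-inf. Name that AUC consistently with Table 5, which the sponsor must check because the table is redacted in the public copy.
4. Delete the F2, F3 and any pooled CRV431-versus-placebo contrasts of PK parameters. If stage matters for PK, describe it among CRV431-treated subjects by dose.
5. Remove the placebo denominator from 12.3.3, and state that placebo is the comparator for safety and biomarker endpoints only.

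The cost is protocol and SAP wording. No new data, samples or patients are needed.
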